Treatment with external beam radiation therapy (EBRT) is the standard of care for patients with localized bone pain, and results in the palliation of pain in the majority of these patients. More than 66% of patients with a limited number of well-localized bony metastases can be treated effectively by external-beam irradiation. However, approximately 30% of patients treated with radiation therapy do not experience pain relief [8, 12-16]. Furthermore, there is an increased risk of pathologic fracture in the peri-irradiation period due to an induced hyperemic response at the periphery of the tumor. This weakens the adjacent bone and increases the risk of spontaneous fracture. Adding to this, patients who have recurrent pain at a site previously irradiated may not be eligible for further radiation therapy secondary to limitations in normal tissue tolerance. The speed of response to radiation therapy varies; most symptomatic bony metastases begin to respond over the course of 10 to 14 days, 70% of patients experience some pain relief within 2 weeks of starting therapy and, within 3 months 90% of the responding patients achieve pain relief.

Patients, who had EBRT and failed to improve, may need to seek other therapies such as radio frequency ablation, surgical resection, etc., which are less efficient and have higher treatment related morbidity. Because the ExAblate system is designed to non-invasively ablate tissue, ExAblate may meet the need of these EBRT failed patients. The ExAblate system has the potential to achieve the first three of the four above mentioned goals, as well as changing the treatment limits and resulting morbidity in accordance with the above-mentioned goals [17]. The palliative effect of ExAblate is achieved by heating the bone periosteum, thus ablating the sensory origin of the pain and has the potential to achieve some tumor control.

Based on the FDA approved phase-1 initial study (IDE # G050177) results and the results of the study that was performed outside the United States that the sponsor has done, palliation effects are significant in terms of mean improvement, the percent of treated patients who reported symptomatic improvement and in the treatment durability.

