To assess the impact of bone pain following targeted/localized treatment on health-related quality of life, the pain interference scale from the BPI-QoL will be included [**Appendix E**]. Pain interference refers to the extent to which pain interferes with day-to-day functioning and is more likely to be sensitive to anticipated changes in the health-related quality of life among the study population. The most common measure of cancer pain interference is the BPI -QoL[30]. This is a validated scale consisting of 7 items that ask respondents to indicate the extent to which pain interferes with general activity,

¹ Meds increase is defined as a change of 25% ¹or more in MEU; per Chow, E., et al., International consensus on palliative radiotherapy endpoints for future clinical trials in bone metastases. Radiother Oncol, 2002. 64(3): p. 275-80

mood, walking ability, normal work, relations with other people, sleep, and enjoyment of life”.

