2.4 Study End Points

Safety

A full safety profile will be developed for the ExAblate treatment of bone metastases. All adverse events will be captured and summarized as defined in **Section-6.2**. Adverse events (type, frequency, severity) are expected to be similar to those captured for the original PMA study (PMA # P110039).

For his study, the Safety comparison with the data of the Pivotal (IDE Study G070022) study will be descriptive with no statistical endpoints.

Efficacy

A full efficacy profile will be developed for the ExAblate treatment of bone metastases. For this study efficacy will be determined by comparing outcomes at the 3 month visit to baseline within subjects. Additionally the safety and efficacy of treatment Responders and Non-Responders will be tabulated, and compared with that of the original PMA (P110039).

The primary endpoint is the proportion of responders at the 3 month study visit.

Definition of terms:

- Patient Responders: these are all ExAblate treated patients who experience at least a 2 point improvement from baseline on NRS at the treated site without increase in medications
- Patient Non-Responders: these are all ExAblate treated patients who experience less than 2 points improvement from baseline to 3 months on the NRS at the treated site without increase of medication or increased medications.
- Patient Pain Progression: these are all ExAblate treated patients who either experience 2 points worsening from baseline to 3 months on the NRS at the treated site or who increase morphine equivalence 25% or more. Pain progression is a subset of non-responders.

Secondary Endpoints

This study has two secondary end points. The goal of these secondary end points is to assess the impact of the ExAblate treatment of painful bone Mets on the overall quality of life and clinical benefits to ExAblate MRgFUS treated patients:

Quality of life outcomes of all treated patients will be captured during the course of the study. A comparison between baseline and 3 months post-ExAblate treatment of the BPI-QoL will be performed.

Pain Medications of all patients will be captured and summarized. Changes in narcotic medications will be expressed in morphine equivalents.

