Study Enrollment at 50% Complete — As it was communicated to the agency during the PMA process as well as during the actual IDE study, the enrollment rate in the pivotal IDE study at US sites was approximately 0.07 subjects per month per site. The rate of enrollment was very slow partly because of the terminally ill patient population and their limited life expectancy, and partly because this particular patient population is heavily managed by their oncologists who tend to rely on pain medications and existing familiar technologies. However, in the pivotal IDE study, patients had the opportunity to receive an experimental palliative treatment that was not otherwise available. Now, since the PMA has been approved, patients can elect the ExAblate treatment without participating in the PAS; there may be less of an incentive to participate in the PAS than in the IDE study. Regardless, InSightec will use its best efforts to maintain a similar rate of enrollment in the PAS study as in the IDE study. Based on the pivotal study enrollment rate of 0.07, 1 site enrolled by 2 months, and adding 2 sites each 4 months to a total site enrollment of 10 sites (7 sites by the 6th month and 10 by the 14th month), the 70th subject would be enrolled by the 105th month of the study.

InSightec will continuously consider the possibility of increasing the number of participating sites; however, because of the large capital equipment investment and long installation time, it is expected that the number of sites that could be added to the study each year will be very limited, and would not meaningfully contribute to the increased rate of enrollment. Nonetheless, all newly installed sites will be offered an opportunity to participate in the PAS in an effort to maximize enrollment.

Final Study Report—Study results will be reported within 6 months of completion. Based on the timeline above, this is expected to be approximately 8 years and 10 months after full approval of the study.

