6.4 Criteria for Removal from the Study

Subjects can be exited from the study at any time if in the opinion of the principal investigator it is not in the best interest of the patient to carry on as planned. In Addition, patient may also chose to exit the study to pursue other alternative treatment options.

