Any UADEs will be reported to the Sponsor and to the reviewing IRB as soon as possible. However, in no event must this report be made later than two (2) working days after the PI learns of the incident.

Other common non-study or non-device related, minor health complaints will not be collected as AE's (for example: colds, sprains, headaches). Patients who have a progression of their primary disease or symptoms that lead to an alternative treatment will not be reported as an AE.

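### Pain relief from a further local treatment of the study lesion before month 3 is scored as an ExAblate response when the patient stays in the study

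*Combined protocol and SAP*

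**What the plan says.** Protocol section 2.4 makes the responder proportion at month 3 the primary endpoint: "The primary endpoint is the proportion of responders at the 3 month study visit". Responders are the treated patients "who experience at least a 2 point improvement from baseline on NRS at the treated site without increase in medications". The footnote to section 2.3 defines the medication part: "Meds increase is defined as a change of 25" per cent or more in morphine-equivalent units (MEU). Pain progression needs either a 2-point worsening at the treated site "or who increase morphine equivalence 25% or more". Section 5.2 tests responders (P10) against patients who worsen (P01).

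Several other places come near the question:
- **Section 3.2**, inclusion 11 and exclusion 16, limits radiation to the target lesion before study treatment only.
- **Section 4.3**, step 21, allows a second session to complete the plan and rules out a repeat for continued pain. It gives no score for a breach and does not mention other modalities.
- **Section 5.3** applies LOCF to missing visits.
- **Section 6.4** makes leaving the study optional: "In Addition, patient may also chose to exit the study to pursue other alternative treatment options".
- **Section 4.4 and Table 1** list NRS, BPI, KPS, analgesics, symptoms, general health and adverse events at follow-up. They list no item for local procedures at the treated site.
- **Section 6.5**, on disease progression, adds "symptoms that lead to an alternative treatment will not be reported as an AE".

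**The concern.** The plan accepts that relief obtained by other means should not be credited to the device. More analgesic disqualifies a responder, and bisphosphonates must stay stable throughout. Local therapy to the study lesion is a more direct confounder, and it has no such rule after treatment.

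Re-treatment is plausible. The patients have intractable pain, the plan expects 30% to progress, and section 1.2 says that patients whose radiotherapy failed "may need to seek other therapies such as radio frequency ablation, surgical resection". Those re-treated after ExAblate will mostly be those in whom it failed. Each successful rescue takes a patient out of P01 or out of the stable group, and may add one to P10. With no control arm, nothing offsets this in the primary endpoint or in the only formal test.

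**Working it through.** **1. Does any rule change the score?** Take a patient who is worse at month 1, has the lesion irradiated, stays in the study and attends month 3 with NRS 2 points below baseline and MEU not raised by 25% or more. Section 2.4 scores a responder. Radiation, surgery and ablation do not enter MEU, so the medication condition is not triggered. Month 3 is observed, so LOCF does not apply. The patient did not exit, so section 6.4 does not apply. Nothing in 2.4 or Section 5 alters the score.

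**2. The plan's own figure.** Inputs from section 5.2: P10 = 0.60, P01 = 0.30, one-sided alpha 0.025, n = 65, stated power 0.70. I used the exact McNemar test:

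rejection = sum over m of Bin(m; n, P10 + P01) x Pr[Bin(m, P10/(P10 + P01)) >= c(m)],

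where m is the number of discordant patients and c(m) is the smallest r with Pr[Bin(m, 1/2) >= r] <= 0.025. Power at n = 65 is 0.693, and the smallest n reaching 0.70 is 67. The stated 65 is reproduced within 2 patients.

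**3. Effect of re-treatment.** The documents give neither a re-treatment rate nor a rescue success rate for this population. Assumptions:
- share of progressors re-treated, s = 10%, 20% or 30%;
- rescue success, k = 30% or 66%; the upper value is the external-beam figure in section 1.2;
- true parity, P10 = P01 = 0.40, with 20% stable.

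The proportion moved is x = P01 x s x k. If a rescue produces a response, P10 becomes 0.40 + x and P01 becomes 0.40 - x. If it only brings the patient back to stable, P10 stays at 0.40 and P01 becomes 0.40 - x. Rejection at n = 65, against 0.018 when x = 0:

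| s | k | x | to response | to stable only |
|---|---|---|---|---|
| 10% | 30% | 0.012 | 0.031 | 0.024 |
| 20% | 30% | 0.024 | 0.049 | 0.031 |
| 30% | 30% | 0.036 | 0.075 | 0.040 |
| 10% | 66% | 0.026 | 0.053 | 0.032 |
| 20% | 66% | 0.053 | 0.127 | 0.055 |
| 30% | 66% | 0.079 | 0.255 | 0.090 |

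In patients, x runs from 0.012 x 65 = 0.8 to 0.079 x 65 = 5.1.

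At the planned 60% v 30%, the highest case moves 0.30 x 0.30 x 0.66 = 0.059. That gives 65.9% v 24.1%, and power rises from 0.693 to 0.948.

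**4. How few patients matter.** The planned result in 65 patients is about 39 v 20 (0.60 x 65 = 39; 0.30 x 65 = 19.5), one-sided exact p = 0.009. If three of the 39 are rescored as non-progressing non-responders, the result is 36 v 20, p = 0.022; if four are, it is 35 v 20, p = 0.029, which misses 0.025. If the rescored patients had already progressed before re-treatment, two are enough: 37 v 22, p = 0.034.

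**The case against.** The best case on the other side concerns size and evidence, and much of it stands.

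- **The 66% is from other patients.** Section 1.2 gives it for limited, well-localised metastases treated with external-beam radiation. This study enrols patients whom radiation did not adequately relieve, those whose physician would not prescribe it or more of it, and those who refuse more. The same section calls the remaining options less efficient. The 66% rows are therefore upper bounds.
- **Progression to response is a long way.** A patient 2 points worse must fall by at least 4 points, and one whose MEU rose must bring it back under the threshold. Many rescues would reach only stable, hence the last column.
- **Some patients will leave.** Those who exit for other treatment fall under section 5.3. The gap concerns those who stay, and the documents do not say how many that would be.

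A reader might also infer more than the text supports:
- *That the data could not reveal re-treatment.* Section 6.5 governs adverse event reporting only, and the CRFs (Appendix C) are not in the text. What can be said is that the visible schedule states no capture of local therapy.
- *That enrolled patients would get repeat ExAblate elsewhere.* The remark in section 5.4 that "patients can elect the ExAblate treatment without participating in the PAS" explains slow enrolment; it does not describe patients already in the study.
- *That a nerve block escapes in the same way.* Section 4.3 treats it as local medication, so the medication condition may reach it, although the MEU footnote leaves this unclear.

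None of this supplies the missing scoring rule.

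**Conclusion.** The concern holds for patients who stay in the study and have the treated lesion irradiated, operated on or ablated again before month 3. The definition as written credits their relief to ExAblate, and the bias favours the device.

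The size cannot be known from the documents. Under the assumptions above, false-positive rejection is 0.031-0.075 at 30% rescue success and 0.024-0.090 if rescues reach only stable, against 0.018 without re-treatment and a nominal 0.025. The 0.26 should not be quoted as an estimate: it needs 30% of progressors re-treated, 66% success and every success moving from progression to response. The sample size itself is not in error on this point.

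A reader might conclude that every re-treated patient belongs in P01. The documents do not support that. Section 2.4 defines progression by NRS or MEU, and a stable patient who is re-treated has met neither condition. It would also be costly: at 60% v 30%, moving 5% of patients from stable to P01 (60% v 35%) cuts power from 0.69 to 0.49.

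**What to change.** In section 2.4 and Section 5, state for the primary analysis that a treated patient who receives radiation, surgery or ablation to the treated lesion for pain, after the completed study treatment and before the 3-month assessment, is a Non-Responder whatever the month-3 NRS. Class pain progression (P01) for that patient from the last NRS and MEU before the re-treatment, using the existing definition. A completing second session under section 4.3, step 21, does not count as re-treatment.

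Add one item to the follow-up CRFs, if not already there: local therapy to the treated site since the last visit, with type and date. Report the number of such patients. Show two sensitivity analyses: the as-observed result, and the result with all re-treated patients counted in P01.

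The cost is a short text change and one item at four existing visits. The responder proportion may be somewhat lower, and power falls if re-treatment is common: if 5% of patients move from responder to non-progressing non-responder (55% v 30%), exact power at n = 65 falls from 0.69 to 0.55. The change concerns scoring and data capture only, not which treatment patients may receive. It should be made before data accrue, because procedures that were not recorded are hard to recover later.

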2.5 Case Report Form Data

The study data will be collected electronically versus the traditional paper CRF entry method. This electronic data capture (EDC) complies with the current guidance of 21 CFR Part 11, Electronic Records and Signatures.

3 DESCRIPTION OF PATIENT POPULATION

3.1 Patient Selection

Patients with bone lesion(s):

- Who have failed radiation therapy. Radiation failure patients are those who have received radiation without adequate relief from metastatic bone pain as determined by the patient and treating physician, those for whom their treating physician would not prescribe radiation or additional radiation treatments, and those patients who refuse additional radiation therapy.
- That appears to be metastatic disease or multiple myeloma by clinical and or imaging techniques with known history of malignancy.
- Who have persistent intractable pain from a well defined tumor site.
- Who have a fracture risk score ≤ 7 , will be eligible for this study

3.2 Subject Enrollment

- a) Information concerning eligibility for the study will initially be taken from the patient's case history. Patients who appear to be eligible will be asked if they would like to participate in this study.
- b) Written informed consent will be obtained from each participating patient prior to collecting a patient history, other testing. The patient will be counseled concerning the research nature of this study, and the risks and possible benefits to participation. This

study will utilize a pre-treatment imaging exam to confirm the diagnosis, and to estimate tumor size, location, and access for treatment. Participation is fully voluntary.

Inclusion Criteria

1. Men and women age 18 and older
2. Patients who are able and willing to give consent and able to attend all study visits
3. Patients who are suffering from symptoms of bone metastases or multiple myeloma bone lesions:

Patients who have received radiation without adequate relief from metastatic bone pain as determined by the patient and treating physician, those for whom their treating physician would not prescribe radiation or additional radiation treatments, and those patients who refuse additional radiation therapy.

4. Patient with NRS (0-10 scale) pain score ≥ 4 irrespective of medication
5. Targeted bone/tumor interface are ExAblate device accessible and are located in ribs, extremities (excluding joints), pelvis, shoulders and in the posterior aspects of the following spinal vertebra: Lumbar vertebra (L3 – L5), Sacral vertebra (S1 – S5)
6. Targeted bone/tumor interface (most painful lesion) size up to 55 cm^2 in surface area
7. Patient whose targeted (treated) lesion is on bone and the interface between the bone and lesion is deeper than 10-mm from the skin.
8. Targeted (treated) tumor clearly visible by non-contrast MRI, and ExAblate MRgFUS device accessible
9. Able to communicate sensations during the ExAblate treatment
10. Patients on ongoing chemotherapy regimen at the time of eligibility:
 1. with same chemotherapy regime (as documented from patient medical dossier),
And
 2. Worst pain NRS still ≥ 4
And
 3. do NOT plan to initiate a new chemotherapy for pain palliation should be eligible for the study.

Note: Planned multiple courses of chemotherapy are not considered New Chemotherapy.

11. No radiation therapy to targeted (most painful) lesion in the past two weeks
12. Bisphosphonate intake should remain stable throughout the study duration.
13. Patients will have from 1 to 5 painful lesions and only the most painful lesion will be treated.
14. Patients with persistent distinguishable pain associated with 1 site to be treated (if patient has pain from additional sites, the pain from the additional sites must be evaluated as being less intense by at least 2 points on the NRS compared to the site to be treated).

Exclusion Criteria

1. Patients who either
 - Need surgical stabilization of the affected bony structure (>7 fracture risk score, see Section 7.4)

OR

 - Targeted tumor is at an impending fracture site (>7 on fracture risk score, see Section 7.4).

OR

 - Patients with surgical stabilization of tumor site with metallic hardware
2. More than 5 painful lesions, or more than 1 requiring immediate localized treatment
3. Targeted (treated) tumor is in the skull
4. Patients on dialysis
5. Patients with life expectancy < 3-Months
6. Patients with an acute medical condition (e.g., pneumonia, sepsis) that is expected to hinder them from completing this study.
7. Patients with unstable cardiac status including:
 - Unstable angina pectoris on medication
 - Patients with documented myocardial infarction within six months of protocol entry
 - Congestive heart failure requiring medication (other than diuretic)
 - Patients on anti-arrhythmic drugs
8. Severe hypertension (diastolic BP > 100 on medication)
9. Patients with standard contraindications for MR imaging such as non-MRI compatible implanted metallic devices including cardiac pacemakers, size limitations, etc.

10. Patients with an active infection or severe hematological, neurological, or other uncontrolled disease.
11. Known intolerance or allergies to the MRI contrast agent (e.g. Gadolinium or Magnevist) including advanced kidney disease
12. KPS Score < 60 (See “Definitions” below)
13. Severe cerebrovascular disease (multiple CVA or CVA within 6 months)
14. Individuals who are not able or willing to tolerate the required prolonged stationary position during treatment (approximately 2 hrs.)
15. Target (treated) tumor is less than 1cm from nerve bundles, bowels or bladder.
16. Patients initiating a new chemotherapy regime for pain purposes only, or radiation (for the targeted most painful lesion) within the last 2 weeks

Note: Planned multiple courses of chemotherapy are not considered New Chemotherapy.

17. Patients unable to communicate with the investigator and staff.
18. Patients with persistent undistinguishable pain (pain source unidentifiable of the targeted lesion)
19. Patient whose bone-lesion interface is < 10-mm from the skin
20. Targeted (most painful) tumor NOT visible by non-contrast MRI,
21. Targeted (most painful) tumor Not accessible to ExAblate
22. The targeted tumor is less than 2 points more painful compared to other painful lesions on the site specific NRS.

4 INVESTIGATION PLAN

4.1 Study Design

This is a prospective, multi-site, one-arm study for evaluating the safety and effectiveness of ExAblate treatment of metastatic bone tumors. Prospective study patients will sign the informed consent, complete study questionnaires and be evaluated in terms of inclusion exclusion criteria. Patients not meeting the study criteria will be exited from the study as screen failures and not included in analyses. All qualifying patients will complete a baseline CT scan, and in the event the CT scan is already available, then it should not be more than 3-months old; should an MR exam be available, it should be also considered (baseline MRI is not requested). Any patients not meeting study criteria at imaging will be exited as screen failures.

Study Optimization Protocol:

Because the standard of care requires physicians to address pain when present and this specific patient population is suffering from painful metastases, the vast majority of patients referred to this study may already be receiving various pain medication regimens. The Inclusion/Exclusion criteria of the protocol require patients to have functionality at study entry of KPS ≥ 60 . In most instances, patients with a KPS = 60 at enrollment will be considered to be on an optimized pain medications regimen. Patients not previously on opioids pain medications will be required to proceed to optimization option-1 OR optimization option-2 as described below:

OPTION – 1: THIS OPTION COMBINES PAIN STABILIZATION WITH FUNCTIONALITY

Patients will start on a regimen similar to the NCCN guidelines while maintaining the level of function defined in the protocol (KPS ≥ 60). NCCN guidelines require frequent assessment and re-evaluation of moderate to severe pain generally every 24-48 hours and with long-acting agents after 5 half lives. Study specific forms have been developed to document interventions taken to optimize pain control and to document patient response in regard to impact on pain and function due to medication-related adverse events. Once it has been determined that pain control has been optimized such that a further increase in narcotics:

- is not expected to result in a significant reduction in pain, defined as a 2 point or greater decrease on the NRS,

OR

- that interventions for pain control have resulted in a 10 point or greater decline in KPS

OR

- that commonly recognized opioid-related side effects achieve Grade 3 or greater opioids related AE

The NRS scale will be used to assess changes in pain and the KPS will be used to assess function. Opioid-related side effects will be collected using “Common Terminology Criteria for Adverse Events v4.0 (CTCAE)” (<http://ctep.cancer.gov>) as a guideline for AE terminology and grade (severity) assessment. Patients meeting any one of the above 3 criteria, and still meeting the study Inclusion/Exclusion requirements, specifically NRS ≥ 4 and KPS ≥ 60 , will proceed to the ExAblate.

OPTION – 2: THIS OPTION DETERMINES PAIN STABILIZATION

All Patients who choose to follow Option-2 will be followed for pain stability for at least 1-week. Patients will be counseled to maintain their medication intake unchanged during this period. Daily capture of NRS pain score and medication intake will be performed at the same time of each day. At the end of this period, a patient will be declared on a stable NRS if the NRS Score remains stable during this period; i.e., no more than 2 points change from baseline.

All patients failing this stabilization routine will be followed for another week. All patients failing two consecutive weeks of this routine will be exited from the study and declared as screen failures.

The NRS scale will be used to assess changes in pain and the KPS will be used to assess function. Opioid-related side effects will be collected using “Common Terminology Criteria for Adverse Events v4.0 (CTCAE)” (<http://ctep.cancer.gov>) as a guideline for AE terminology and grade (severity) assessment.

Patients passing the above stabilization criteria, and still meeting the study Inclusion/Exclusion requirements, specifically NRS ≥ 4 and KPS ≥ 60 , will proceed to the ExAblate treatment.

